3.1.1 Modified Designs

Bladder Cancer Cohort

The enrollment for the BC cohorts N and N-I (Dose Level 2b) will be conducted as a One Stage Design:

- Recently, inhibition of PD-L1 by MPDL3280A was shown to have clinical activity in patients with metastatic urothelial bladder cancer, leading to approval of the drug in this indication by the FDA.⁸⁸ The overall response rate in all treated subjects was 15%.
- Nivolumab has recently demonstrated meaningful antitumor activity with an overall response rate of 19.6% in all treated subjects
- As these data show that checkpoint inhibition has potential to be an active treatment for patients with advanced bladder cancer, a Two Stage design with the intent of avoiding to expose too many patients to a potentially ineffective treatment does not appear to be necessary for this specific tumor type.⁶⁶

- Bladder arms N and N-I (Dose Levels 2 and 2b) will be conducted as a One Stage Design with the treatment of 26-105 subjects in each arm. The Safety Evaluation Phase for the N-I arm will start at Dose Level 2 (nivolumab 1 mg/kg, ipilimumab 3 mg/kg) and will evaluate safety and tolerability after the first 6 randomized subjects. Following the N-I safety evaluation phase, Dose Levels 2 will treat approximately 92 subjects and 2b will treat up to a total of 105 subjects. Based on the safety evaluations thus far on study, no dose escalation phase is necessary for bladder cohort N-I Dose Level 2b (nivolumab 3 mg/kg, ipilimumab 1 mg/kg).

Ovarian Cancer Cohort

The OC cohorts N-I (Dose Level 2, 2b, 2c) will be conducted as a One Stage Design with the enrollment of 40 subjects in each arm. The Dose Level 2c was added to Ovarian Cancer Cohort based on the results of CA209003 and CA209012 clinical studies mentioned above. The efficacy and tolerability of nivolumab monotherapy observed in CA209003 study with longer follow-up of previously treated NSCLC patients suggested a strategy in which nivolumab serves as the “base” of a combination regimen, with ipilimumab exposure limited by lower doses and/or less frequent administration. This strategy is the basis for new nivolumab and ipilimumab combination regimens with nivolumab 3 mg/kg Q2W combined with ipilimumab 1 mg/kg Q6W. This regimen was used in CA209012 study with preliminary data showing a promising activity and a good safety profile of the combination.

The enrollment to the N-I arm to Dose Levels 2, 2b, and 2c will be conducted simultaneously. Due to the low risk of development of new safety signals on the combination arms confirmed by the additional information from the combination studies in melanoma, lung, renal cell carcinoma, and glioblastoma as well as the clinical study with ipilimumab 10 mg/kg monotherapy in ovarian cancer, which did not reveal any new safety signals (please refer to [Section 1.1](#) Study Rationale and Sections 5.5.1.2, 5.5.2.2, 5.5.3.2, 5.5.4.2, and 5.6.1.3 in the current version of the Investigator Brochure), no Safety Evaluation Phase will be employed. Ovarian cancer subjects will be followed for related toxicities and decisions to stop treatment will be made on an ongoing basis.

Additional Pancreatic Cancer Cohort

Enrollment in the PC cohort will be initiated for one dose level N-I in combination with cobimetinib (Dose Level 2d) and will be conducted as a One-Stage Design:

The safety profile of all agents proposed for the triplet combination are well defined as either monotherapy or in combination and the products are already commercially available for the treatment of several advanced and metastatic tumor types. The safety profile of the combination of nivolumab with ipilimumab (3 mg/kg) is well characterized and it is approved for treatment of unresectable or metastatic melanoma. The toxicity profile of the nivolumab + ipilimumab combination has been shown to correlate with the ipilimumab dose: With increasing doses of ipilimumab there has been an increase in frequency of adverse events, and potentially the severity of these events, however no novel toxicities have been demonstrated versus either agent

alone.^{82,89,90,91,92} In the current regimen for this protocol cohort, the dose of ipilimumab will be cumulatively lower than on prior cohorts studied in the proposed indication as well as the approved dose level for the combination for the treatment of advanced and metastatic melanoma. The toxicity profile with lower doses of ipilimumab has been established to be very similar to that of nivolumab monotherapy.⁹³

The safety of a PD-L1 agent combined with cobimetinib is already established and safe. For the triplet combination, non-overlapping toxicities are expected. Therefore, if there were to be an increase in toxicity, no new toxicities are anticipated and it is not expected to be significantly different than that seen in the combination of nivolumab with the higher dose of ipilimumab, which has already been demonstrated to be tolerable.

Safety of the triplet combination in the proposed indication will be monitored continuously on a daily basis by the Medical Monitor, and enrollment will be staggered given the timing of amendment approval differ at individual sites as well as the limited number of eligible patients available at each site. No more than 6 patients will be enrolled in the first week of the study with subsequent enrollment of ≤ 6 subjects per week during the first month. A scheduled safety review by the Medical Monitor will occur after 12 patients are treated and have been followed for at least 1 month and regular safety telephone conferences will be performed with the investigators participating in studying the triplet combination in the proposed indication.

3.1.2 Dose-Escalating Safety Evaluation Phase for Arm N-I

The combination of 1 mg/kg nivolumab + 3 mg/kg ipilimumab is already approved for the treatment of advanced and metastatic melanoma regardless of BRAF mutational status and has more recently been tested in NSCLC and RCC. This regimen is expected to also be tolerable in the tumors being studied in this protocol. However, as an added safety precaution, the combination of N-I will first be assessed in a dose escalating safety phase. This safety evaluation will be conducted for each of the investigated tumor types independently (Table 3.1.2-1). Recently, data from Phase 1/2 studies in NSCLC and RCC have shown, that the dose level of 1 mg/kg ipilimumab plus 3 mg/kg nivolumab is well tolerated while potentially preserving the tumor efficacy.^{9,10} Therefore, a Dose Level 2b (nivolumab 3 mg/kg, ipilimumab 1 mg/kg) will be investigated in the Dose-Escalating Safety Evaluation Phase in case Dose Level 2 is not tolerable for any of the tumor types being studied.

Table 3.1.2-1: Dose Cohort for Arm N-I

Dose Cohort Level	Nivolumab (mg/kg)	Ipilimumab (mg/kg)
-1	0.3	1
1	1	1
2	1	3
2b	3	1

The first dose cohort will be Level 1. If this is deemed tolerable, then Level 2 will be initiated. If Level 1 is not tolerable, then Level -1 will be initiated. The BC cohort will start at Level 2. If Dose Level 2 is not tolerable for a certain tumor type, Dose Level 2b will be investigated. There will be no dose escalation beyond Level 2 or Level 2b. Once the highest dose level for further investigation has been confirmed in the Dose-Escalating Safety Evaluation Phase, Arm N-I will continue enrolling with Stage 1 ([Section 3.1.3](#)).

Subjects on active treatment need to be followed up for at least 6 weeks after start of study treatment before determination of the tolerability of a dose level. However, tolerability beyond 6 weeks may also be taken into consideration. The criteria for tolerability ([Table 3.1.2-2](#)) are based on drug related adverse events leading to permanent discontinuation (listed in [Section 4.5.5](#)) and include:

- If none of the first 3 subjects in a given dose level permanently discontinue treatment due to study drug related adverse events within the first 6 weeks, then this dose cohort will be deemed as tolerable. For Dose Cohort Level 2 or Dose Cohort Level 2b, at least 6 subjects need to have been exposed to this dose level and followed up for at least 6 weeks after start of study treatment before the enrollment will proceed in Stage 1. The enrollment of these 6 subjects will occur in a staggered mode, first 3 subjects will be enrolled and followed up for at least 6 weeks before the next 3 subjects will be enrolled and followed up for at least 6 weeks.
- If one or two of the first 3 subjects in a dose cohort permanently discontinue treatment within the first 6 weeks due to study drug related adverse events, this cohort will be expanded to 6 subjects.
- If one of 6 subjects in a dose cohort permanently discontinue treatment due to study drug related adverse events within the first 6 weeks, then dose cohort will be deemed as tolerable.
- If two of 6 subjects in a dose cohort permanently discontinue treatment within the first 6 weeks due to study treatment related adverse events, this cohort may be expanded to 9 subjects. If an expansion is not possible because of the severity of the adverse events leading to permanent discontinuation, then this dose cohort will be deemed not tolerable.
- If no more than two of 9 subjects in a dose cohort permanently discontinue treatment due to study treatment related adverse events within the first 6 weeks, then this dose cohort will be deemed as tolerable.
- If at least three of the first 9 subjects in a dose cohort permanently discontinue treatment within the first 6 weeks due to study treatment related adverse events, a Dose -1 Cohort (in case of toxicities at Dose Level 1) or a Dose 2b Cohort (in case of toxicities at Dose Level 2) may proceed.

For the decision to enroll a Dose -1 or Dose 2b Cohort, the clinical severity of the adverse events leading to permanent discontinuation in the previous Dose Cohort will be taken into consideration.

Table 3.1.2-2: Dose Cohort for Arm N-I

Number of subjects treated and followed up for at least 6 weeks after start of study treatment	Number of subjects with permanent discontinuation due to treatment related adverse events	Next Step
3	0	Dose tolerable
3	1-2	Expand to 6 subjects
6	≤ 1	Dose tolerable
6	2	Expand to 9 subjects
9	≤ 2	Dose tolerable
9	≥ 3	Dose not tolerable ^a

^a discussion with investigators to review risk/benefit taking into account reversibility of AEs and depth of response

3.1.2.1 Evaluation of Risk/Benefit for Doses that do not meet Tolerable Criteria

In the event of ≥ 3 of the first 9 subjects requiring permanent discontinuation, a discussion with investigators may be held to review the risk/benefit of this regimen. The rationale for this evaluation is that the most frequent severe drug related AEs for the combination in melanoma have been asymptomatic, reversible laboratory events (ie, LFTs and lipase) and there is preliminary evidence of deep and durable responses in the N-I arm in advanced melanoma (CA209004). Therefore, a discussion of the risk/benefit of the regimen will be triggered if the following criteria are met:

- A majority of subjects who discontinue due to treatment related AEs have deep tumor response (ie, $> 80\%$ reduction)
- All treatment related AEs leading to discontinuation are non-fatal, reversible and without severe sequela (ie, GI perforation)
- A majority of the treatment related AEs are laboratory in nature, asymptomatic, and monitorable via routine blood draws

If a decision is made to continue with a regimen because of a favorable risk/benefit profile (ie, non-fatal AEs in subjects with near CRs that are durable) and despite meeting the ‘not tolerable’ criteria above, then IRBs must be notified, ICFs must be updated, and discussion of the risk/benefit must be documented with all future subjects who enroll on this regimen.

3.1.3 Staged Enrollment (Stage 1 and Stage 2)

3.1.3.1 Stage 1

This Stage is intended to assess the efficacy in 18 subjects per treatment arm per tumor type to determine whether enrollment should continue to Stage 2. For efficacy determination, each Arm within each tumor type will be assessed independently.

Arm N: The enrollment and treatment of 18 subjects to Arm N per tumor type can begin while the initial Dose Cohort for Arm N-I in this tumor type is still ongoing. The dose level in Arm N is 3 mg/kg nivolumab IV every two weeks (Q2W). This dose has been established in more than 700 subjects with various tumor types exposed to nivolumab monotherapy with a tolerable AE profile. Therefore no dose adjustments for Arm N are planned.

Arm N-I: Up to 18 subjects will be enrolled and treated in this arm per tumor type at the highest tolerated Dose Level determined during the Dose Escalating Safety Evaluation phase. The 3-9 subjects treated at the highest dose level confirmed for further investigation from the Dose Escalating Safety Evaluation phase will be counted as part of the 18 required subjects.

3.1.3.2 Criteria to proceed from Stage 1 to Stage 2

The decision to proceed from Stage 1 to Stage 2 will be made for each tumor and for each treatment arm independently and include ([Table 3.1.3.2-1](#)):

- 2 or more of 18 subjects in a given arm must have confirmed PR or CR before enrollment for that arm will be continued in Stage 2. The tolerability of the regimen will continue to be evaluated by the Sponsor with the investigators to ensure that it is acceptable for continued enrollment.
 - Subjects with initial PD per RECIST 1.1 who continue treatment in their initially assigned treatment arm beyond progression ([Section 4.5.7](#)) and subsequently reach confirmed immune related CR or PR (relative to initial tumor assessment) and including any new measurable lesions within the sum of all target lesions, will be considered as having an objective response for the purposes of meeting criteria for moving from Stage 1 to Stage 2. Although not standard RECIST 1.1, these immune related response criteria using unidimensional measurements account for the unusual immune related tumor response patterns reported for both ipilimumab and nivolumab.
- Once the last subject in a given treatment arm has permanently discontinued treatment for any reason or has reached the Week 48 Tumor Assessment, and the above criteria are not met, then this treatment arm will not proceed to Stage 2. Ongoing subjects will continue to be followed up for efficacy and safety.
- In case that 2 or more of subjects in a given arm enrolling in Stage 1 have confirmed PR or CR, but the enrollment of 18 subjects for Stage 1 has not been completed or 18 subjects have been enrolled but have not been randomized and started treatment at that timepoint, the following applies:
 - Arm N: the enrollment for that arm can be continued in Stage 2. The tolerability of the regimen will continue to be evaluated by the Sponsor with the investigators to ensure that it is acceptable for continued enrollment.
 - Arm N-I: at least 9 subjects need to have been exposed to the highest dose level which has been confirmed for Stage 1 and followed up for at least 6 weeks after start of study treatment before the enrollment for that arm can be continued in Stage 2. The tolerability of the regimen will continue to be evaluated by the Sponsor with the investigators to ensure that it is acceptable for continued enrollment.

Table 3.1.3.2-1: Efficacy criteria to proceed from Stage 1 to Stage 2

Efficacy criteria	Next Step
2 or more of 18* subjects in a given arm have confirmed PR or CR	Go into Stage 2
1 or no of 18* subjects in a given arm have confirmed PR or CR.	No Go into Stage 2

* see [Section 3.1.3.2](#) last bullet point for further clarification

3.1.3.3 Stage 2

Arm N: For treatment **Arm N** of the given tumor type that continues to Stage 2, additional subjects will be assigned to a total of 40 subjects, inclusive of those enrolled in Stage 1. For tumor types where nivolumab monotherapy proceeded to Stage 2, assessment of Dose Level 2b in Stage 2 (nivolumab 3 mg/kg + ipilimumab 1 mg/kg, n=40 subjects) will be initiated for that tumor type. A separate evaluation of Dose Level 2b may be necessary if the safety and tolerability of Dose Level 2 has not been confirmed.

Arm N-I (Dose Level 2): In case treatment Arm N-I at Dose Level 2 proceeds to Stage 2, additional subjects will be assigned to a total of 40 subjects at Dose Level 2, inclusive of those enrolled in Stage 1. In order to investigate the Dose Level 2b with a potentially better tolerability while preserving tumor efficacy, an additional 40 subjects at Dose Level 2b will be enrolled once Arm N-I Dose Level 2 proceeds to Stage 2. In this case, a separate safety evaluation of Dose Level 2b is not necessary, as the safety and tolerability of Dose Level 2 had already been confirmed previously.

Within a given tumor type, the treatment arms can proceed to Stage 2 independent of the status of the other treatment arm.

For Stage 2, upon completion of enrollment of the initial 40 subjects, additional subjects may be assigned into Arm N and Arm N-I up to a total of 100 subjects (including those assigned in Stage 1) in each treatment arm of the given tumor type. For tumor types where nivolumab monotherapy or nivolumab 1 mg/kg plus ipilimumab 3 mg/kg proceeded to Stage 2, assessment of Dose Level 2b in Stage 2 (nivolumab 3 mg/kg + ipilimumab 1 mg/kg, n=up to 70 subjects) may be initiated for that tumor type.

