Two Stage Design: GC, PC, TNBC, or SCLC Arms N and N-I will follow a two-stage design to test whether nivolumab monotherapy or nivolumab combined with ipilimumab yields an objective response rate (ORR) that is of clinical interest in the investigated tumor types. For each tumor type, only treatment arms which meet an ORR threshold will proceed from Stage 1 to Stage 2 (described in protocol [Section 3.1.4](#)). Enrollment to Stage 2 in a given treatment arm can continue even if the other treatment arm is still in Stage 1.

Table 1: Efficacy criteria to proceed from Stage 1 to Stage 2

Efficacy criteria	Next Step
2 or more of 18 subjects in a given arm have confirmed PR or CR	Go into Stage 2
1 or no of 18 subjects in a given arm have confirmed PR or CR.	No Go into Stage 2

For Stage 2, upon completion of enrollment of the initial 40 subjects, additional subjects may be assigned into Arm N and Arm N-I up to a total of 100 subjects (including those assigned in Stage 1) in each treatment arm of the given tumor type. For tumor types where nivolumab monotherapy or nivolumab 1 mg/kg plus ipilimumab 3 mg/kg proceeded to Stage 2, assessment of Dose Level 2b in Stage 2 (nivolumab 3 mg/kg + ipilimumab 1 mg/kg, n=up to 70 subjects) may be initiated for that tumor type. For SCLC, an additional 250 subjects (second- or third-line) will be randomized in a 3:2 ratio to one of the 2 expansion groups: nivolumab 3 mg/kg every 2 weeks or nivolumab 1 mg/kg + ipilimumab 3 mg/kg every 3 weeks for 4 cycles followed by nivolumab 3 mg/kg.

Modified Design for Bladder Cancer Cohort:

Bladder arms N and N-I (Dose Levels 2 and 2b) will be conducted as a One Stage Design with the treatment of 26-105 subjects in each arm. The Safety Evaluation Phase for the N-I arm will start at Dose Level 2 (nivolumab 1 mg/kg, ipilimumab 3 mg/kg) and will evaluate safety and tolerability after the first 6 randomized subjects. Following the N-I safety evaluation phase, Dose Level 2 will treat approximately 92 subjects and 2b will treat up to a total of 105 subjects. Based on the safety evaluations thus far on study, no dose escalation phase is necessary for bladder cohort N-I Dose Level 2b (nivolumab 3 mg/kg, ipilimumab 1 mg/kg).

Modified Design for Ovarian Cancer Cohort:

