The primary endpoint of this study, ORR, is based on tumor assessments at baseline and then at 6 weeks from first dose. Tumor assessments continue every 6 weeks for the first 24 weeks and every 12 weeks thereafter while on treatment or on treatment hold for any reason until disease progression (investigator-assessed RECIST 1.1-defined progression) or treatment discontinuation, except for subjects treated beyond progression or who discontinued treatment for other reasons than PD.

Statistical Considerations:

Sample Size Determination

Sample size determination in the original protocol

This study comprises a Dose Escalating Safety Evaluation Phase for the Combination Arm, followed by a Staged Enrollment for Arm N, and Arm N-I.

In the original protocol, gastric cancer, small cell lung cancer, triple negative breast cancer, and pancreatic cancer are included and the Staged Enrollment Part utilizes a modified Simon two-stage design with the treatment of 40 subjects to evaluate whether nivolumab, or the combination of nivolumab/ipilimumab yields an objective response rate (ORR) that is of clinical interest. In this study, an ORR of 10% or less is considered not of clinical value, and an ORR of 25% or greater is considered of strong clinical interest. The modified Simon design evaluates the null hypothesis that the true response rate is $\leq 10\%$ versus the alternative hypothesis that the true response rate is $> 10\%$. The 2-stage testing within each cohort targets a Type I error rate of 5% and has 80% power to reject the null hypothesis if the true response rate is 25%.

Sample size determination for bladder cancer cohort

In Amendment 06, the bladder cohort is added. A one stage design with the treatment of 60-100 subjects is used for nivolumab monotherapy and the dose level 2b. These sample sizes will provide 90% to 97% power to reject the null hypothesis of 10% response rate if the true response rate is 25% with a two-sided Type I error rate of 5%.

In Amendment 14, the dose level 2 arm (nivolumab 1 mg/kg + ipilimumab 3 mg/kg) of the bladder cancer cohort is to enroll and treat a total of 92 subjects. A one stage design will be used. Based on a 19.6% ORR for nivolumab monotherapy (CA209275), the sample size of 92 in this arm will provide 93% power to reject the null hypothesis of 19.6% response rate if the true response rate is 35% with a two-sided Type I error rate of 5%.

Sample size determination for SCLC expansion cohort

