1.1.11 Rationale for Permitting Continued Treatment in Select Cases of Progressive Disease

Accumulating clinical evidence indicates some subjects treated with immune system stimulating agents may develop progression of disease (by conventional response criteria) before demonstrating clinical objective responses and/or stable disease. This phenomenon was observed in approximately 10% of subjects in the Phase 1 study of nivolumab and has also been reported for ipilimumab monotherapy.⁸⁴ Two hypotheses have been put forth to explain this phenomenon. First, enhanced inflammation within tumors could lead to an increase in tumor size which would appear as enlarged index lesions and as newly visible small non-index lesions. Over time, both the malignant and inflammatory portions of the mass may then decrease leading to overt signs of clinical improvement. Alternatively, in some individuals, the kinetics of tumor growth may initially outpace anti-tumor immune activity. With sufficient time, the anti-tumor activity will dominate and become clinically apparent. Therefore, subjects will be allowed to continue study therapy after initial investigator-assessed RECIST 1.1 defined progression if they are assessed to be deriving clinical benefit and tolerating study drug ([Section 4.5.7](#)). Such subjects must discontinue study therapy upon evidence of further progression.

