8 STATISTICAL CONSIDERATIONS

8.1 Sample Size Determination

Sample Size determination in the original protocol

This study comprises a Dose Escalating Safety Evaluation Phase for the Combination Arm, followed by a Staged Enrollment for Arm N and Arm N-I.

In the original protocol, gastric cancer, SCLC, TNBC, and pancreatic cancer are included and the Staged Enrollment Part utilizes a modified Simon two-stage design⁹⁵ with the treatment of 40 subjects to evaluate whether nivolumab or the combination of nivolumab/ipilimumab yields an objective response rate (ORR) that is of clinical interest. In this study, an ORR of 10% or less is considered not of clinical value, and an ORR of 25% or greater is considered of strong clinical interest. The modified Simon design evaluates the null hypothesis that the true response rate is $\leq 10\%$ versus the alternative hypothesis that the true response rate is $> 10\%$. The 2-stage testing within each cohort targets a Type I error rate of 5% and has 80% power to reject the null hypothesis if the true response rate is 25%.

Sample Size determination for bladder cancer cohort

In Amendment 06, the bladder cohort is added. A one stage design with the treatment of 60 - 100 subjects is used for nivolumab monotherapy and the dose level 2b. These sample sizes will provide 90% to 97% power to reject the null hypothesis of 10% response rate if the true response rate is 25% with a two-sided Type I error rate of 5%.

In Amendment 14, the dose level 2 arm (nivolumab 1 mg/kg + ipilimumab 3 mg/kg) of the bladder cancer cohort is to enroll and treat a total of 92 subjects. A one stage design will be used. Based on a 19.6% ORR for nivolumab monotherapy (CA209275), the sample size of 92 in this arm will provide 93% power to reject the null hypothesis of 19.6% response rate if the true response rate is 35% with a two-sided Type I error rate of 5%.

Sample Size determination for SCLC expansion cohort

In Amendment 09, in addition to the original two-stage design in the SCLC cohort, additional SCLC expansion cohort subjects will be randomized in a 3:2 ratio to one of two expansion groups: Arm A (150 subjects, nivolumab mono 3 mg/kg q2w) or Arm B (100 subjects, nivolumab 1 mg/kg + ipilimumab 3 mg/kg q3w) and will be stratified by number of prior treatment lines (1 vs 2 prior chemotherapy regimens).

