8.3.1 Primary Endpoint(s)

The primary endpoint is the objective response rate (ORR). The ORR is defined as the number of subjects with a best overall response (BOR) of complete response (CR) or partial response (PR) divided by the number of treated subjects. The BOR is defined as the best response designation, as determined by the investigator or BICR for selected tumor types, recorded between the date of randomization or treatment assignment and the date of objectively documented progression per RECIST 1.1 or the date of subsequent anti-cancer therapy, whichever occurs first. CR or PR determinations included in the BOR assessment must be confirmed by a second scan no less than 4 weeks after the criteria for response are first met. For subjects without documented progression or subsequent therapy, all available response designations will contribute to the BOR assessment. For subjects who continue treatment beyond progression, the BOR should be determined based on response designations recorded up to the time of the initial RECIST 1.1-defined progression.

For the SCLC expansion cohort, the estimated difference along with its corresponding p-value of ORR assessed by BICR between nivolumab monotherapy and nivolumab / ipilimumab combination therapy (nivolumab 1 mg/kg + ipilimumab 3 mg/kg) will be provided. In addition, 95% CI (two-sided) will also be presented for the estimated difference of ORR between nivolumab monotherapy and nivolumab / ipilimumab combination therapy.

Similar methods will be used to summarize ORR for each stratification factor (no p-value will be provided).

ORR will be further characterized by the duration of response (DOR) and the magnitude of reduction in tumor volume. DOR will be computed for subjects with a BOR of PR or CR and is defined as the time from first confirmed response (CR or PR) to the date of the first documented tumor progression as determined using RECIST 1.1 criteria or death due to any cause, whichever occurs first. For subjects who neither progress nor die, the DOR will be censored using the same censoring algorithm as used for PFS in Section 8.3.2. The magnitude of reduction in tumor volume is defined as the percent decrease in tumor volume from baseline to nadir, observed up until the time of the first documented tumor progression or death.

These measures of response will be interpreted in the context of historical responses observed following treatment with approved agents.

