8.4.2 Efficacy Analyses

8.4.2.1 Primary Endpoint Methods

The efficacy analyses will be performed on the all treated population. ORR will be summarized for each cohort by a binomial response rate and corresponding two-sided 95% exact CI using the method proposed by Atkinson and Brown⁹⁶ for cohorts using two-stage design and the Clopper-Pearson method for cohorts using the one stage design⁹⁷.

For SCLC expansion cohort, the estimated difference along with its corresponding p-value of ORR assessed by BICR between nivolumab monotherapy and nivolumab/ipilimumab combination therapy (nivolumab 1 mg/kg + ipilimumab 3 mg/kg) will also be presented with 95% CI. Similar methods will be used to summarize ORR for each stratification factor. However the p-value will not be provided for each stratification factor.

DOR as determined by the investigator or BICR for selected tumor types will be summarized for subjects who achieve confirmed PR or CR using the Kaplan-Meier (KM) product-limit method. The median value, along with two-sided 95% CI using the Brookmeyer and Crowley method,

will also be calculated by cohort. In addition, the percentage of responders still in response at different time points (3, 6, and 12 months) will be presented based on the KM plot.

The magnitude of reduction in tumor burden will be summarized descriptively. Immune related responses will be summarized descriptively.

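### An arm can enter Stage 2 on immune-related responses that the primary ORR never counts, and the prescribed Atkinson-Brown interval then has no limits for 0 or 1 of 40 and is too wide for other low counts

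*Protocol*

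**What the plan says.** - **Design (8.1 and synopsis).** The original four tumor types use a "modified Simon two-stage design with the treatment of 40 subjects". On the hypotheses, "an ORR of 10% or less is considered not of clinical value, and an ORR of 25% or greater is considered of strong clinical interest". On error rates, "The 2-stage testing within each cohort targets a Type I error rate of 5% and has 80% power to reject the null hypothesis". No final cut-off and no early-stopping probability is given.
- **Gate (synopsis Table 1; 3.1.3.2).** The arm goes on if "2 or more of 18 subjects in a given arm have confirmed PR or CR". The text of 3.1.3.2 adds that a subject who progresses by RECIST 1.1, stays on treatment and then reaches a confirmed immune-related CR or PR "will be considered as having an objective response for the purposes of meeting criteria for moving from Stage 1 to Stage 2". It acknowledges that this departs from RECIST 1.1 and gives the reason.
- **Primary endpoint (8.3.1).** For subjects treated beyond progression, "the BOR should be determined based on response designations recorded up to the time of the initial RECIST 1.1-defined progression".
- **Interval (8.4.2.1).** Two-stage cohorts get a two-sided 95% exact interval "using the method proposed by Atkinson and Brown"; one-stage cohorts get Clopper-Pearson. Immune-related responses are summarized descriptively.

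**The concern.** The same subject can be a responder at the gate and a non-responder in the ORR. That alone is a choice a sponsor may make in a signal-detection study. The difficulty is the interval. Atkinson-Brown orders the outcomes of a two-stage trial and treats every arm with 0 or 1 responders among 18 as stopped. Under 3.1.3.2 such an arm may instead continue to 40, and that outcome lies outside the sample space on which the interval is built.

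Two things follow. If the final RECIST count is 0 or 1 of 40, no Atkinson-Brown limits exist, so the instruction in 8.4.2.1 cannot be carried out. If the final count is low but at least 2, limits exist, but the method ranks the result above a stop at 1 of 18. The upper limit for that stop is 27.3%, so no Stage 2 result, however poor, can exclude the 25% target. What is at stake is how the primary endpoint is reported for the weakest arms that went on.

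**Working it through.** **Inputs.** From the protocol: null ORR 10%, target 25%, 18 then 40 subjects, go at 2 or more. Two assumptions: (a) the final cut-off, not stated, is inferred below; (b) q, the proportion of subjects who respond only by immune-related criteria, is not given and is taken as 2%, 5% and 10%. Section 1.1.11 says of progression before later benefit: "This phenomenon was observed in approximately 10% of subjects in the Phase 1 study of nivolumab". That figure includes later stable disease, so 10% is an upper reference.

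**Reproducing the design.** With X1 ~ Bin(18, p) and Z ~ Bin(22, p), reject if X1 ≥ 2 and X1 + Z ≥ r.

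| r | type I error at 10% | power at 25% |
|---|---|---|
| 7 | 9.3% | 88.6% |
| 8 | 4.05% | 80.7% |
| 9 | 1.5% | 69.4% |

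Only r = 8 meets the stated 5% and 80%, so 8 of 40 is the inferred cut-off.

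**Probability of the path.** Entering Stage 2 with at most 1 RECIST responder has probability P(Bin(18, p+q) ≥ 2) − P(Bin(18, p) ≥ 2). At p = 10%:
- q = 2%: 0.654 − 0.550 = 0.104
- q = 5%: 0.776 − 0.550 = 0.226
- q = 10%: 0.901 − 0.550 = 0.351

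**Probability of no limits (final count 0 or 1 of 40).** With Y the immune-related-only responders in Stage 1, this is P(X1=0, Y≥2)·P(Z≤1) + P(X1=1, Y≥1)·P(Z=0). At p = 10%, q = 5%: 0.0396 × 0.3392 + 0.1866 × 0.0985 = 0.0318. For q = 2% and 10% it is 1.2% and 5.7%. At p = 5% it is 5.2%, 14.1% and 26.4%.

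**The limits.** For a final count s, the Atkinson-Brown lower limit solves P(X1≥2, S≥s) = 0.025 and the upper solves P(X1≤1) + P(X1≥2, S≤s) = 0.025.

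| s of 40 | Atkinson-Brown | Clopper-Pearson |
|---|---|---|
| 0 or 1 | none | defined (upper 8.8%, 13.2%) |
| 2 | 1.4–27.3% | 0.6–16.9% |
| 3 | 2.1–27.4% | 1.6–20.4% |
| 4 | 3.2–27.9% | 2.8–23.7% |
| 5 | 4.5–29.2% | 4.2–26.8% |
| 8 | 9.1–35.9% | 9.1–35.6% |

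At 2, 3 and 4 of 40 only Clopper-Pearson excludes 25%. By 8 of 40 the two nearly agree.

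**Error rates under the mixed gate.** With 8 of 40, type I error moves from 4.05% to 4.09%, 4.13% and 4.17% for q = 2%, 5% and 10%. Its ceiling is the single-stage value, 4.19%. One-sided miss rates were enumerated over X1, Y and Z (ranges over q = 2% to 10%; outcomes without limits are shown separately and not counted as misses). The switched rule uses Clopper-Pearson on 40 when X1 ≤ 1 and the arm continued, and Atkinson-Brown otherwise.

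| true ORR | no A-B limits | A-B: truth below / above | switched: truth below / above |
|---|---|---|---|
| 3% | 7.5–42.1% | 2.3–2.9% / 0 | 2.1–2.2% / 0 |
| 5% | 5.2–26.4% | 1.3–1.4% / 0 | 1.3–1.4% / 0 |
| 10% | 1.2–5.7% | 1.5% / 0 | 1.5% / 0.1–0.9% |
| 20% | 0.03–0.11% | 1.9% / 0.6–1.7% | 1.9% / 1.1–1.8% |
| 25% | about 0.01% or less | 1.2% / 0.2–0.5% | 1.2% / 0.7–0.8% |

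Over a grid of true ORRs from 0.5% to 40%, the switched rule's largest miss rates are 2.49% and 2.37%. Conditional on the path, its upper limit falls below the truth 17% to 18% of the time at a true ORR of 25%, where the path itself has probability 1.3% to 3.5%.

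**The case against.** The gate rule is deliberate, disclosed and reasoned, and immune-related responses get their own descriptive summary. In a signal-detection study it is fair to let such activity open Stage 2. That stands. The gate is also largely applied already: 3.1.4 records that the SCLC arms have proceeded. Rewriting it would be retrospective.

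A reader might infer that the futility stop breaches the design, because an arm at 10% RECIST ORR passes 65% to 90% of the time instead of 55%. The arithmetic is right, but the protocol promises no early-stopping probability, q is assumed, and an arm with confirmed shrinkage after progression is not plainly inactive. A reader might also infer an inflated false-positive rate; the final test stays at or below 4.19%.

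On the interval, it is fair to reply that where limits exist Atkinson-Brown keeps each miss rate within 2.5% at the ORRs checked from 5% to 25%. A slight excess appears only at very low rates, such as 2.9% at a true ORR of 3% with q = 10%. So general under-coverage is not the defect. Nor is Clopper-Pearson exact for this path, as its conditional miss rate shows.

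The n = 18 and n = 40 figures are also idealized: 3.1.3.2 lets Stage 2 open before 18 are treated, and 3.1.3.3 lets arms grow to 100.

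Finally, edge-case rules often sit in an SAP. But here the protocol itself names the gate, the endpoint and the interval method, and the three do not fit together.

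**Conclusion.** The point holds as an interval problem confined to arms that enter Stage 2 with fewer than 2 RECIST responders. For them the prescribed 95% interval rests on a sample space that excludes what happened. It cannot be computed at 0 or 1 of 40, and at 2 to 4 of 40 it is wide enough to keep the 25% target that Clopper-Pearson excludes. At a true ORR of 10% the path has probability 10% to 35% and the outcome without limits 1% to 6%.

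These sizes rest on an assumed q of 2% to 10%, a final N of 40 and, for the type I figure only, the inferred cut-off of 8. The effect is negligible near 20% to 25% ORR. The documents do not support reading this as type I error inflation, as a broken futility guarantee, or as a general coverage failure of Atkinson-Brown.

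**What to change.** Add one sentence to 8.4.2.1: for any arm that entered Stage 2 with fewer than 2 confirmed RECIST 1.1 responders among its first 18 subjects, the 95% interval for ORR is Clopper-Pearson on the arm's final number of treated subjects. Leave the Stage 2 rule in 3.1.3.2 as it is.

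The change is to analysis text only, so it can still be made after enrollment and alters nothing for subjects. It gives limits for every outcome and, in the n = 40 enumeration, keeps overall miss rates below 2.5% per side. Its cost is lower coverage conditional on that path when the true ORR is high, a combination that seldom occurs; a note in the report can say so.
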